#### 6.4.1. Immunogenicity Assessments

There will be two types of immunogenicity assessments in booster/third dose analysis:

- Serum nAb value against SARS-CoV-2 as measured by pseudovirus and/or live virus neutralization assays.
- Serum bAb value as measured by enzyme-linked immunosorbent assay specific to the SARS-CoV-2 S protein.

#### 6.4.2. Primary Analysis of Antibody-Mediated Immunogenicity Endpoints

Part 1 or Part 2 booster dose:

For Part 1 or Part 2 booster dose primary immunogenicity analysis of GM in children receiving mRNA 1273 booster dose, an analysis of covariance (ANCOVA) model will be performed to assess the difference in the immune response (Ab level) between BD-Day 29 in children receiving mRNA-1273 booster dose in Study P204 and Day 57 in young adults ( $\geq 18$  to 25 years of age) receiving mRNA-1273 primary series in Study P301. In the analysis of covariance model, antibody values at BD-Day 29 for P204 and Day 57 for P301 will be a dependent variable, and a group variable (children in Study P204 and young adults in Study P301) will be the fixed effect. The GMT will be estimated by the GLSM from the model, and its corresponding 95% CI will be provided for each group. The GMR (ratio of GMTs) for children in Study P204 with respect to young adults in Study P301 will be estimated by the ratio of GLSM from the model, and the corresponding 95% CIs will be provided. The 95% CI for GMR will be used to assess the between-group difference in immune response at BD-Day 29 in children in Study P204 compared with Day 57 after the primary vaccine series in young adults in Study P301. The noninferiority of post booster GM in children will be considered demonstrated if the lower bound of the 95% CI of the GMR is  $> 0.667$  based on the noninferiority margin of 1.5. The estimated GMT with 95% CI and GMR with 95% CI will also be provided using t-distribution.

For Part 1 or Part 2 booster dose primary immunogenicity analysis of seroresponse in children receiving mRNA-1273 booster dose, the SRR with 95% CI (using Clopper-Pearson method) will be summarized. The SRR difference with 95% CI (using Miettinen-Nurminen score method) to compare post-booster SRR at BD-Day 29 in children in Study P204 with the primary series SRR at Day 57 (28 days after Dose 2) in adults ( $\geq 18$  to 25 years of age) in Study P301 will be computed. The SRR is defined as a value change from baseline (pre-Dose 1) below the LLOQ to  $\geq 4 \times$  LLOQ, or at least a 4-fold rise if baseline is  $\geq$  LLOQ. The noninferiority of SRR in children receiving mRNA-1273 booster dose will be considered demonstrated if the lower bound of the 95% CI of the SRR difference is  $> -10\%$  based on the noninferiority margin of 10%.

Booster dose primary immunogenicity objective for an age group in Part 2 will be considered to be met if the noninferiority in the age group compared with the young adults ( $\geq 18$  to 25 years of age) is demonstrated based on both coprimary endpoints.

### Part 3:

For Part 3 primary series primary immunogenicity analysis of Ab GM in children 6 years to  $< 12$  years of age receiving mRNA-1273 25  $\mu$ g which is half of the 50  $\mu$ g dose level

used in Part 2 for the same age group, the GM in children compared with young adults  $\geq 18$  to 25 years of age from Study P301 will be assessed using ANCOVA model. The estimated GMT with 95% CI and GMR with 95% CI will also be provided using t-distribution.

For Part 3 third dose primary immunogenicity analysis of GM in children receiving a third mRNA-1273 dose, an ANCOVA model will be performed to assess the difference in the immune response at BD-Day 29 in children receiving mRNA-1273 third dose in Study P204 compared with Day 57 in young adults ( $\geq 18$  to 25 years of age) receiving mRNA-1273 primary series in Study P301. In the ANCOVA model, antibody values at BD-Day 29 in P204 children and values at Day 57 in P301 young adults will be a dependent variable, and a group variable (children in Study P204 and adults in Study P301) will be the fixed effect.

The P301 comparator in SAP for Part 3 immunogenicity analysis is young adults  $\geq 18$  to 25 years of age instead of protocol P301 comparator  $\geq 18$  years of age, because the originally planned hypothesis testing in protocol for part 3 will not be performed due to the small number of participants enrolled in Part 3, which is insufficient to power the hypothesis testing. All the immunogenicity analyses for Part 3 will be descriptive. In these descriptive analyses, the comparator will be young adults  $\geq 18$  to 25 years of age from P301 instead of  $\geq 18$  years of age to be consistent with the comparator group in immunogenicity analyses in part 1 and part 2 of the study.

The GMT will be estimated by the GLSM from the model and its corresponding 95% CI will be provided for each group. The GMR for children in Study P204 with respect to adults in Study P301 will be estimated by the ratio of GLSM from the model and the corresponding 95% CIs will be provided. The 95% CI for GMR will be used to assess the between-group difference in immune response at BD-Day 29 in children in Study P204 compared with Day 57 following the primary vaccine series in young adults in Study P301.

For Part 3 third dose primary immunogenicity analysis of seroresponse in children receiving a third dose of mRNA-1273, the SRR with (1-alpha) CI (using Clopper-Pearson method) will be summarized, where the 1-alpha can be 95% depending on the alpha level of 0.05. The SRR difference with (1-alpha)% CI (using Miettinen-Nurminen score method) to compare post-third dose SRR at BD-Day 29 in children in Study P204 with the primary series SRR at Day 57 (28 days after Dose 2) in young adults ( $\geq 18$  to 25 years of age) in Study P301 will be computed.

#### **6.4.3. Secondary Analysis of Antibody-Mediated Immunogenicity Endpoints**

In the booster dose analysis for Part 1 and Part 2, the noninferiority of secondary endpoints will be assessed and tested using the same method as primary series of mRNA-1273 in part 1 open-label phase and part 2 blinded phase.

#### **6.4.4. Exploratory Analysis of Antibody-Mediated Immunogenicity Endpoints**

For each group applicable, the following evaluations will be performed at each time point at which blood samples are collected for immunogenicity antibody tests against SAS-CoV-2 prototype or variants of interest as applicable.

- GM level of SARS-CoV-2-specific Ab levels with corresponding 95% CI will be provided at each time point (e.g., Baseline [Pre-dose 1], Day 57, Day 209, Pre-booster/third dose, and BD-Day 29). The 95% CIs will be calculated based on the t-distribution of the log-transformed values then back transformed to the original scale for presentation. GM level will be plotted at each timepoint using boxplot. The following descriptive statistics will be also provided at each time point: the number of subjects (n), median, minimum and maximum.
- GM fold-rise of SARS-CoV-2-specific Ab levels with corresponding 95% CI will be provided at each timepoint over baseline (pre-dose 1) level, and post-booster/third dose timepoint over pre-dose 1 level and pre-booster/third dose level. The 95% CIs will be calculated based on the t-distribution of the log-transformed values then back transformed to the original scale for presentation. The following descriptive statistics will be also provided at each time point: the number of subjects (n), median, minimum and maximum.
- Proportion of subjects with seroresponse due to vaccination relative to pre-dose 1 will be tabulated with 2-sided 95% Clopper-Pearson CIs at each timepoint.

#### **Multiplicity adjustment:**

Please refer to SAP section 6.4.2 in Part 1 open-label phase and Part 2 blinded phase for the hierarchical hypothesis testing to adjust mulplicity to to preserve the family-wise Type I error rate (alpha = 0.05) in part 1 open-label phase and part 2 blinded phase.

The hypothesis testing for the two coprimary endpoints (geometric mean titer [GMT] and SRR) for the primary series of mRNA-1273 in part 2 blinded phase was completed and statistically significant based on data snapshot dated 10 Nov 2021 for 6-<12 years age

group, and was also statistically significant based on data snapshot dated 21 Feb 2022 for 2-<6 years and 6 months -<2 years age group for pseudovirus neutralizing antibody. Thus the alpha level of 0.05 may be passed to Part 2 booster dose analysis hypothesis testing.

In booster phase, the hypothesis testing for the two coprimary endpoints after BD of mRNA-1273 will be tested first at alpha level of 0.05. The alpha 0.05 is preserved for the hypothesis testing for the booster dose primary immunogenicity endpoint in Part 2, starting in the older age group (6 years to < 12 years of age), then the younger age group (2 years to < 6 years and 6 months to <2 years of age combind, at the same dose level). The testing will continue through the sequence only until an endpoint is not statistically significant (did not meet specified noninferiority success criteria of any primary endpoint) in Part 2, in which case the testing will stop. There will be no hypothesis testing for Part 3 due to enrollment early discontinuation, and thus no type I error will be used in Part 3.

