#### 4.1.3. Optional Booster Doses

Per Amendment 7, Part 1 (all ages) and 6 years to < 12 years Part 2 participants will be offered an optional booster dose lower than the chosen primary series for each age group at least 6 months after Dose 2 of mRNA-1273 (Part 1 participants and Part 2 participants in Study Arm 8; Part 2 placebo recipients from Study Arms 9, who crossed over to mRNA-1273 after unblinding).

In Amendment 9, all participants in all age groups in Part 1 and Part 2 who have not yet received a booster dose will be offered a booster dose with mRNA-1273.214 (instead of mRNA-1273).

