2. Refer to Protocol Section 6.1.1 for individual participant criteria for delay of study vaccination.
3. Pregnancy test prior to study injections on D1 and D29 will be a point-of-care urine test and will be performed if deemed appropriate by the investigator. At the discretion of the investigator, a pregnancy test either via blood or point-of-care urine test can be performed at any time during the study.

**8.6. Appendix F: Schedule of Assessments for Optional Booster Doses with mRNA-1273 for Parts 1 and 2, Study Arms 1 Through 9 under Protocol Amendment 7**

| Visit Number   | BD-1               | BD-2                       | BD-2A   | BD-3   |                                |                                | BD-4    | BD-5                          | BD-6    |
|--|--------------------|----------------------------|---|--------|--------------------------------|--------------------------------|---------|-------------------------------|---------|
| Type of Visit  | C                  | SC                         | C   | C      | SFU                            |                                | C       | SC                            | C       |
|  |                    |                            |   |        | eDiary                         | SC                             |         |                               |         |
| Study Visit Day   | BD-D1  | 7 days after BD-D1 (BD-D8) | 14 days after BD-D1 (Sub-Cohort E only and optional) BD-D15 | BD-D29 | Every 4 weeks BD-D43 – BD-D155 | Every 4 weeks BD-D57 – BD-D169 | BD-D181 | 270 days after BD-1 (BD-D271) | BD-D366 |
| Window Allowance (Days)   | 0                  | + 3                        | + 3   | -3/+14 | ± 3                            | ± 3                            | -3/+14  | + 3                           | -3/+14  |
| Days Since Most Recent Vaccination  | 0                  | 7                          | 14  | 28     |                                |                                | 180     | 270                           | 365     |
| Confirm informed consent /assent form booster addendum signing   | X                  |                            |   |        |                                |                                |         |                               |         |

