mRNA = messenger RNA; RT-PCR = reverse transcriptase polymerase chain reaction; SAE = serious adverse event; SARS-CoV-2 = severe acute respiratory syndrome coronavirus 2; SC = safety (phone) call; SFU = safety follow up.

Note: In accordance with FDA Guidance on Conduct of Clinical Trials of Medical Products during COVID-19 Public Health Emergency (DHHS 2020), investigators may convert study site visits to home visits or telemedicine visits with the approval of the Sponsor.

1. A BD may be administered to Part 1 participants (all ages) and 6 to < 12 year old Part 2 participants provided there are no current contraindications for further dosing. A participant who is currently in the Convalescent Period may come in for a BD-1 visit and receive a BD as long they are at least 90 days from initial diagnosis of COVID-19. Applicable participants will be offered a booster at least 6 months (Participants in part 1 and participants 6 to < 12 year old in Part 2) after Dose 2.
2. Symptom-directed physical examination will be performed at the BD-D1. On dosing day before injection, the arm receiving the injection should be examined and the associated lymph nodes should be evaluated. At visits BD-3 (BD-D29), BD-4 (BD-D181) and BD-6 (BD-D366), a symptom-directed physical examination may be performed at the discretion of the investigator. Any clinically significant finding identified during a study visit should be reported as a MAAE. An oral or tympanic temperature should be taken on the day of injection (BD-D1). Participants who are febrile (body temperature  $\geq 38.0^{\circ}\text{C}/100.4^{\circ}\text{F}$ ) before dosing (BD-D1) must be rescheduled to receive the injection. Afebrile participants with minor illnesses can be vaccinated at the discretion of the investigator.
3. Pregnancy test at BD- D1 before the booster dose injection will be a point-of-care urine test and will be performed if deemed appropriate by the investigator. At the discretion of the investigator, a pregnancy test either via blood or point-of-care urine test can be performed at any time during the study.
4. Sample should be collected prior to dosing on BD-D1.
5. Selected subgroups only; for details, see Appendix G. Participants in sub-Cohort E original mRNA-1273 will have a blood sample for CMI and exploratory serology

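### The booster testing sequence is set in Part 2, but its under-6 step can draw only on Part 1 Arms 5 and 7, at most 225 planned children against the 289 behind the stated 90% GM power

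*SAP*

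**What the plan says.** The multiplicity paragraph at the end of Section 6.4.4 of the booster SAP uses the Part 2 label three times:

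- Alpha hand-over: "Thus the alpha level of 0.05 may be passed to Part 2 booster dose analysis hypothesis testing".
- Testing order: "endpoint in Part 2, starting in the older age group (6 years to < 12 years of age), then the younger age group", where the younger group is the two under-6 age groups combined at the same dose level.
- Stopping rule: testing runs until an endpoint fails "in Part 2, in which case the testing will stop".

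The success rule in Section 6.4.2 has the same label: "Booster dose primary immunogenicity objective for an age group in Part 2 will be considered to be met" if both coprimary endpoints show noninferiority.

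Section 4.2 of the booster SAP, like 4.2 of the SAP for Part 1 and the Part 2 blinded phase, takes about 289 per-protocol, pre-booster-negative children in an age group against 289 P301 young adults. It gives 90% power for the GM comparison and makes no exception for the under-6 step.

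Section 4.1.3 says who is offered which booster. Under Amendment 7, "Part 1 (all ages) and 6 years to < 12 years Part 2 participants will be offered an optional booster dose". Under Amendment 9, participants in all age groups "who have not yet received a booster dose will be offered a booster dose with mRNA-1273.214 (instead of mRNA-1273".

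**The concern.** The paragraph that controls a confirmatory test should name a population that can supply its data. Read literally, step 2 of the booster sequence asks for under-6 children from Part 2, and the sampling schedule provides none with BD-Day 29 blood after an mRNA-1273 booster. Children who do have such blood come from Part 1, which the paragraph does not mention. The sample-size section has the same gap: it gives one figure per age group, although the arms that can feed the under-6 step are together smaller than that figure.

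At stake are a clear definition of who is in the last booster test and an honest statement of its power.

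**Working it through.** **Who can supply step 2**

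1. Appendix F of the booster SAP is the schedule for "Optional Booster Doses with mRNA-1273 for Parts 1 and 2, Study Arms 1 Through 9 under Protocol Amendment 7". In Table 1 the younger Part 2 arms are Arms 10 to 13, so they fall outside it. Footnote 1 agrees: "A BD may be administered to Part 1 participants (all ages) and 6 to < 12 year old Part 2 participants".
2. Appendix G, the phlebotomy schedule for this booster, has Part 2 rows for 6 to <12 years only. Part 2 children enrolled at age 5 who turned 6 before boosting have a BD-Day 1 draw and nothing later.
3. Part 2 children under 6 come under the Amendment 9 offer of mRNA-1273.214. Section 2.2.2 gives that product no immunogenicity objective, and Appendix J schedules only a pre-booster sample.
4. Among the under-6 Part 1 arms, Appendix G gives BD-Day 29 blood to Arm 5 and Arm 7. Arms 3 and 4 have none, and Arm 6 has no row.
5. Table 1 plans Arm 5 at 150 and the optional Arm 7 at 75. The ceiling is 150 + 75 = 225, and 225/289 = 78% of the stated size.

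**What other sections say.** The coprimary endpoints (3.3.2), the sample-size text (4.2), criterion a of the booster per-protocol subset (5.3) and the model description (6.4.2) all admit Part 1 as well as Part 2. The sequence paragraph and the success rule do not.

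**Reproducing the stated figure.** Inputs from 4.2: SD of ln titre 1.5, margin 1.5, true GMR 1, 2-sided alpha 0.05, 289 adults.

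n per group = 2 × 1.5² × (1.960 + 1.282)² / (ln 1.5)² = 288, or 289 if the bound is taken as 0.667. This matches the plan.

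Power = Φ( ln 1.5 / [1.5 × √(1/n₁ + 1/289)] − 1.96 ), with ln 1.5 = 0.4055.

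- n₁ = 289: standard error 1.5 × √(2/289) = 0.1248; 0.4055/0.1248 = 3.249; Φ(1.289) = 90.1% (noncentral t 90.0%). The stated 90% is reproduced.

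**The under-6 step at its ceiling**

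- n₁ = 225: standard error 1.5 × √(1/225 + 1/289) = 0.1334; 0.4055/0.1334 = 3.040; Φ(1.080) = 86.0% (noncentral t 85.9%).

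With 289 adults, about 287 children are needed for 90%. With 225 children, 90% would need about 398 adults or an SD of about 1.41.

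**Seroresponse.** With true rates of 95% and 99%, the edge of the plan's 4-point allowance, a 10% margin and a normal approximation, power at n₁ = 225 is about 97%. The shortfall is confined to the GM coprimary.

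**The case against.** The strongest reply is that this is a slip of wording with one possible reading. Arms 5 and 7 both received 25 µg and are the only under-6 arms with BD-Day 29 blood, and the phrase about the same dose level fits them. A statistician executing the plan has no other dataset to choose. That is largely true, and it is why no result is said to change. It does not excuse a confirmatory rule that contradicts the sections around it, in a document that states it prevails over the protocol.

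Second, the success rule in 6.4.2 is literally valid for 6 to <12 years, the one age group with an mRNA-1273 booster in Part 2. This stands: the rule leaves the younger group uncovered and is not false.

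Third, the power sentence in 4.2 is conditional: with 289 children, power is 90%. The sentence is correct arithmetic. But 289 is the only size the plan gives for an age group, and the plan's own schedule cannot deliver it for this step.

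Fourth, 4.2 opens by offering an optional booster to all eligible Part 1 or Part 2 participants, with a dose for each age. This might suggest that younger Part 2 children could contribute. It names no product and adds no BD-Day 29 draw for them.

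Finally, a reader might infer a much larger loss. Borrowing the 25% non-evaluable rate from 4.2 of the other SAP gives 225 × 0.75 ≈ 169 children and about 80% power. That rate was set for the Part 2 primary-series Immunogenicity Subset, a different population under different criteria. The documents do not support it here.

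**Conclusion.** The point holds as a mislabelled confirmatory population with an undeliverable size for one step. The sequence paragraph is wrong for step 2, and the success rule is silent on it. The roughly 289 children and 90% GM power cannot be met there: the planned ceiling is 225 and GM power at that ceiling is about 86%, a loss of some 4 points.

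This rests on planned arm sizes (Arm 7 is optional), on 289 adults, and on 4.2's own SD, margin and GMR. The evaluable number can be expected to be lower, because the booster is optional, pre-booster-positive children and those with major deviations are excluded, and Part 1 children not yet boosted were moved to mRNA-1273.214 by Amendment 9. The documents give no figure for how much lower.

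A reader might go further and infer that the sequence fails to control type I error, or that the under-6 test has no data at all. Neither follows. Step 2 is last, so a mislabel there cannot affect the 6 to <12 years test or inflate error, and other sections show that Part 1 data were intended. No seroresponse shortfall is claimed.

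**What to change.** - In the success rule (6.4.2) and throughout the multiplicity paragraph, including the alpha hand-over, refer to Part 1 or Part 2, as the model description in 6.4.2 already does.
- State that step 1 is 6 to <12 years in Part 2 and step 2 is Part 1 Arms 5 and 7.
- Keep the stopping rule applied to both steps. One clause serves both at present, so it should be broadened and not replaced by the Part 1 arms alone.
- Leave dose eligibility as it is, at the same dose level. An explicit restriction to 10 µg recipients would add an exclusion: dose follows age at boosting, while Appendix G is organised by age at enrolment.
- In 4.2 (and the matching paragraph in 4.2 of the other SAP), limit the 289 and 90% statement to 6 to <12 years. Add that the under-6 step has at most about 225 planned children and at most about 86% GM power against 289 adults.

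The cost is wording only: no new data, visits or analyses. The downside is a stated power below 90% for the under-6 booster comparison.

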## **6.5. Efficacy Analysis**

Exploratory analyses of incidence rates in COVID-19, SARS-CoV-2 infection, and asymptomatic infection will be performed using mITT1 Set. The mITT1 Set for the long-term analysis will be used for the incidence rate analysis in the long term including both the blinded and open-label phases; the mITT1 Set for the booster dose analysis will be used for the incidence analysis in the booster dose phase, unless otherwise specified. Subjects will be included in the vaccination group as defined in Section 6.1. As protocol amendment 9 was implemented in October 2022, no surveillance was conducted thereafter, and, therefore, no incidence rates will be calculated after October 2022.

### **6.5.1. Endpoint Definition/Derivation**

#### **6.5.1.1. Derivation of SARS-CoV-2 Infection**

This is a secondary efficacy endpoint, which is a combination of COVID-19 and asymptomatic SARS-CoV-2 infection for participants with negative SARS-CoV-2 status at baseline (for mRNA-1273 group in long-term analysis), pre-dose 1 of mRNA-1273 (for Placebo-mRNA-1273 group in long-term analysis), or pre-booster dose (for booster dose analysis), the incidence of SARS-CoV-2 infection counted starting 14 days after the second dose of mRNA-1273 in Part 2 open-label phase, and cases counted starting 14 days after the booster dose of mRNA 1273 in booster dose analysis. SARS-CoV-2 infection will be defined in participants with negative SARS-CoV-2 at baseline of each part (pre-dose 1 of mRNA-1273 for long-term analysis or pre-booster dose for booster dose):

- bAb level against SARS-CoV-2 nucleocapsid protein negative (as measured by *Roche Elecsys*) at baseline of each part that becomes positive (as measured by *Roche Elecsys*) post-baseline, OR
- Positive RT-PCR post-baseline.

Derivation of this secondary efficacy endpoint is summarized in Table 1 below.

